PECS/SAP blocks with liposomal bupivacaine improve the Overall Benefit Analgesia Score averaged over the postoperative days 1, 2, and 3. A 20% reduction in OBAS geometric mean, a-priori, was defined as minimal clinically important difference.

Secondary hypotheses:

- (1) PECS/SAP blocks decrease postoperative cumulative opioid consumption over the initial three postoperative days.
- (2) PECS/SAP blocks improve pulmonary mechanics, on each of the postoperative days 1, 2 and 3, from the baseline.

Exploratory Hypothesis:

- (1) PECS/SAP blocks improve the Quality-of-Recovery score averaged over the postoperative days 1 and 3, with a difference of 8 points being considered the minimum clinically important difference.⁵⁴
- (2) PECSII and SAP blocks reduce persistent postoperative surgical pain

Methods

The study will be conducted at the Cleveland Clinic Main Campus with IRB approval and written informed consent from participating patients.

Inclusion Criteria

1. 18-85 years old;
2. Elective MICS for isolated robotically-assisted mitral valve repair via anterolateral thoracotomy approach.

Exclusion Criteria

1. Weight less than 50 kg;
2. Pregnancy or lactation;
3. Emergency surgery and patients transferred from the ICU to the operating room;
4. Redo cardiothoracic surgery or post-operative reoperation within 72 hours of index procedure (including minor chest wall procedures including tube thoracostomy, thoracentesis or percutaneous drain placement);
5. Anticipated endotracheal intubation > 24 hours;
6. Anticipated non-study nerve block that provides analgesia to the intercostal nerves;
7. Active systemic or cardiopulmonary infection;
8. Mechanical circulatory support;
9. Allergy or contraindication to study local anesthetics;
10. Current chronic pain or routine opioid use (patients on chronic enteral opioids like Percocet or Vicodin) in a dose of > 30 mg of morphine-milligram-equivalents for at least 10 days in last 30 days;
11. Poorly controlled psychiatric disorders;
12. Clinically important current neurologic deficit; e.g. spinal cord injury, paralysis of extremity, any neurologic deficit in the region of the block
13. Active liver disease or cirrhosis;
14. Pacemaker generator or breast implants ipsilateral to surgery;
15. Previous participation in this study.
16. eGFR <30 or chronic kidney disease

Study protocol

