Liposomal bupivacaine dosing is not weight-based and the full 266-mg bottle can be administered to adult thoracic patients. A maximum of 150 mg bupivacaine HCL can be mixed with Exparel. This equates to one 30-mL bottle of 0.5% bupivacaine HCL or two (2) bottles of 0.25% bupivacaine HCL. If a higher volume of the local anesthetic is needed a 10 ml of normal saline can be added to the mixture of bupivacaine HCL and liposomal bupivacaine. Thus patients ≥ 60 kg will receive 150 mg of bupivacaine HCL, while patients weighing < 60 kg need to have the bupivacaine dose calculated but can still receive full 20 ml of Exparel.

Patients randomized to standard analgesia technique will be given parenteral opioids (such as fentanyl or hydromorphone) until they are converted to the enteral medications such as Percocet.

Study Measurements

Patent demographics will be collected from preoperative interviews and chart review (Table 1). Cumulative opioid consumption, non-opioid analgesics, and length of stay will be

captured electronically using Epic and/or PHDS. Other secondary and descriptive outcome data as well as surgical and intraoperative data will be collected prospectively (Table 2).

Data will be obtained from the following sources: The Society of Thoracic Surgeons (STS) database, Cardiovascular Information Registry (CVIR) of the Heart and Vascular Center at the Cleveland Clinic, the electronic medical record (EPIC), and the electronic Anesthesia Record Keeping System (ARKS).

a) OBAS score

The OBAS score questionnaire (Table 3) will be obtained and score calculated by the research team on post-operative days 1-3. We will calculate the average of the OBAS scores obtained. The OBAS score is a validated postoperatively calculated, multi-dimensional questionnaire that consists of 7 items (Table 3) encompassing not only scale-rated pain score but different aspects of analgesia benefits, side effects and overall patient's satisfaction.⁵³

The OBAS score is based on 7 questions and ranges from 0 to 28 points that will be administered on POD 1 – POD 3. Although these are longitudinal ordinal data, we will be able to treat OBAS scores as continuous data in the analyses with the lower score correlating with better resolution of the analgesia treatment. A 20% reduction in OBAS geometric mean, a-priori, was defined as minimal clinically important difference..^{57,58}

b) Pain assessments

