We will estimate the PECS/SAP blocks effect on OBAS scores using a repeated measures linear regression model with an autoregressive correlation structure, adjusting for ALL imbalanced confounders (if any). Based on these model we would be able to claim if the PECS/SAP blocks had any effect on the OBAS score compared to standard routine analgesia during any of the postoperative time up to third postoperative day. Due to non-normality of OBAS score, it will be log-transformed for analysis. We will report model based P-value and the geometric mean ratio for OBAS scores along with confidence intervals. To assess whether the PECS/SAP blocks effect is heterogeneous over three postop days, we will assess the treatment-by-time interaction using a significance criterion of 0.20. If it appears that the treatment effect is heterogeneous, we will report the treatment effect separately for each postoperative day POD 1, POD 2 and POD 3 using a Bonferroni correction as appropriate (e.g., 0.05/3; 3 postoperative days).

Secondary Analysis

Morphine equivalents will be calculated based on the conversions specified in Table 4 below. Total opioid consumption as well as intraoperative and postoperative day 1, 2, and 3 totals will be collected and converted to milligram morphine equivalents. Patients will not be provided opioid patches for pain relief because there is no known conversion to morphine equivalents. Cumulative opioid consumption data is typically right skewed, so we will normalize it for analyses using a log transformation. Opioid consumption will be reported separately for postoperative day (POD) 0 after surgery, POD 1, POD2, and POD3. We will estimate the effect of PECS/SAP blocks to standard routine analgesia on log cumulative opioid consumption using a repeated measures linear regression model with an autoregressive correlation structure, adjusting for any imbalanced baseline or surgical characteristics between groups.

To assess whether the effect of PECS/SAP blocks is heterogeneous over time, we will assess the treatment-by-time interaction using a significance criterion of 0.20. If it appears that the treatment effect is heterogeneous, we will report the treatment effect separately for each postoperative day using a Bonferroni correction as appropriate (e.g., 0.05/3; 3 postoperative days).

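### The autoregressive covariance with a model-based p-value can misstate the primary standard error, and the three-day OBAS contrast is left undefined

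*Combined protocol and SAP*

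**What the plan says.** The primary hypothesis is that the blocks "improve the Overall Benefit Analgesia Score averaged over the postoperative days 1, 2, and 3". Under Study Measurements, the OBAS item adds: "We will calculate the average of the OBAS scores obtained". The score "ranges from 0 to 28 points that will be administered on POD 1 – POD 3", so there are three repeated measures per patient.

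The Primary analysis section models log OBAS with a "repeated measures linear regression model with an autoregressive correlation structure" and states: "We will report model based P-value and the geometric mean ratio for OBAS scores along with confidence intervals". It then says "we will assess the treatment-by-time interaction using a significance criterion of 0.20", with day-specific effects reported only if the effect looks heterogeneous.

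The Secondary Analysis section uses the same structure for opioids ("log cumulative opioid consumption using a repeated measures linear regression model with an autoregressive correlation structure") and for the three spirometry outcomes.

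The plan does not state the order of the autoregression (first order is assumed here), a robust standard error, a degrees-of-freedom method, a covariance sensitivity analysis, or how the overall effect is formed from the three days.

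**The concern.** There are two separate issues.

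1. **Standard error.** A first-order autoregressive structure, AR(1), does not estimate the POD 1 to POD 3 correlation; it sets it to the square of the one-day correlation. Lasting differences between patients, such as pain sensitivity or reporting style, could plausibly hold it above that. The model-based standard error would then be too small, and the primary p-value and interval too favourable. With three days and 196 patients the restriction is not needed.

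2. **Day weights.** A common treatment effect fitted under AR(1) does not weight the days equally. If the daily effects differ, the reported ratio is then not the three-day average that the hypothesis names.

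**Working it through.** **Step 1. The plan's own figure.** Inputs from Sample Size Considerations: CV 50%, ratio 0.80, two-sided 0.05, 90% power.
- Log SD = sqrt(ln(1 + 0.50²)) = 0.4724, and |ln 0.80| = 0.2231.
- n per group = 2 × 0.4724² × (1.960 + 1.282)² / 0.2231² ≈ 94.2, so 95. The noncentral-t version gives 96, or 192 in total, as stated.
- Table A implies an inflation of (3.26890/3.24152)² = 1.017, where 3.24152 is the fixed-design drift 1.95996 + 1.28155 (to rounding). 192 × 1.017 = 195.3, so 196, as stated.

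The sizing treats OBAS as one measurement per patient. No between-day correlation enters it, and none is given elsewhere, so the correlations below are assumptions.

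**Step 2. Day weights in a common-effect AR(1) fit with complete data.** The weights are (1, 1−ρ, 1)/(3−ρ). POD 2 receives (1−ρ)/(3−ρ):
- ρ = 0.3: 0.7/2.7 = 26%
- ρ = 0.5: 0.5/2.5 = 20%
- ρ = 0.7: 0.3/2.3 = 13%

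If treatment-by-day terms are kept and the three effects are averaged equally, POD 2 gets exactly one-third, even under AR(1).

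**Step 3. Standard error, three days, equal daily variances.** The inverse AR(1) matrix has a zero in the POD 1 to POD 3 position, so the two-day correlation r2 does not enter the likelihood and the fitted ρ settles at the one-day correlation r1. In units of one day's variance:
- model variance = (1+ρ)/(3−ρ)
- true variance = w′Sw, with w from Step 2 and S the true correlation matrix
- type I error = 2[1 − Φ(1.96 × SE_model/SE_true)]

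| r1 / r2 | Model var. | True var. | SE ratio | Type I error |
|---|---|---|---|---|
| 0.5 / 0.25 (exact AR(1)) | 0.600 | 0.600 | 1.000 | 5.0% |
| 0.5 / 0.30 | 0.600 | 0.616 | 0.987 | 5.3% |
| 0.6 / 0.45 | 0.667 | 0.698 | 0.977 | 5.5% |
| 0.6 / 0.50 | 0.667 | 0.715 | 0.965 | 5.8% |
| 0.3 / 0.3 (exchangeable) | 0.481 | 0.539 | 0.945 | 6.4% |
| 0.5 / 0.5 (exchangeable) | 0.600 | 0.680 | 0.939 | 6.6% |
| 0.8 / 0.8 (exchangeable) | 0.818 | 0.884 | 0.962 | 5.9% |
| 0.5 / 0.15 | 0.600 | 0.568 | 1.028 | 4.4% |
| 0.6 / 0.25 | 0.667 | 0.628 | 1.030 | 4.4% |

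A 20,000-run simulation at N = 196 gave 6.4 to 6.5% for exchangeable correlations of 0.3 to 0.7. Using the equal-weight contrast but keeping AR(1) still leaves 5.5 to 6.1% for exchangeable 0.2 to 0.8. The two issues therefore need separate cures.

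**Step 4. Opioids, if all four reported periods (POD 0 to 3) are modelled.** The weights become (1, 1−ρ, 1−ρ, 1)/(4−2ρ). At exchangeable 0.5, model variance = 1.5/3 = 0.500, true variance = 0.5 + 0.5 × (2.5/9) = 0.639, and SE ratio = 0.885, so type I error is 8.3%. Over 0.3 to 0.7 it is 7.6 to 8.3%. At 1.25% (Bonferroni for four outcomes, in the Secondary Analysis section) it is 2.4 to 2.7%. The general Statistical analysis text gives 0.0167 instead; at that level the 0.5 case gives 2 × [1 − Φ(2.394 × 0.885)] = 3.4%.

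**Step 5. What unequal weights do to the ratio.** Assume AR(1) with ρ = 0.5, 98 per group and log SD 0.4724:

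| Daily ratios | AR(1)-weighted | Equal average | Chance the 0.20 test flags it |
|---|---|---|---|
| 0.80 / 0.70 / 0.90 | 0.816 | 0.796 | 99% |
| 0.80 / 0.75 / 0.85 | 0.809 | 0.799 | 66% |
| 0.80 / 0.85 / 0.80 | 0.810 | 0.816 | 39% |

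**Step 6. The alternative.** With an unstructured covariance, treatment-by-day terms and the equal-weight contrast, simulated type I error was 4.8 to 5.1% at N = 196 and 4.9 to 5.1% at N = 66 under every covariance tried. If AR(1) with ρ = 0.6 is exactly true, the equal-weight variance is (3 + 4×0.6 + 2×0.36)/9 = 0.680 against an optimum of 1.6/2.4 = 0.667. That is 2% in variance, or 1% in SE.

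**The case against.** The strongest reply is that the documents establish neither a biased standard error nor a wrong estimand.

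- **Direction and size.** A reader might infer that the test is anti-conservative. No between-day correlation is given, the 6.6% figure needs no decay at all between POD 1 and POD 3, and faster decay makes the test conservative. This stands: the error is modest and its sign is unknown.
- **Weights.** A reader might infer that the plan gives POD 2 far less than one-third. That needs a common-effect fit, which the plan suggests by reporting days separately only under heterogeneity but never states. It also needs a correlation of about 0.5 or more. What stands is that the contrast is undefined.
- **The interaction test.** If the daily effects are equal, any weights estimate the same ratio, and the 0.20 criterion catches most large differences. This limits the problem without removing it: differences the test often misses shift the ratio by about 0.01.
- **Model-based p-value.** The phrase may mean only the p-value from the fitted model. A robust standard error is not excluded, but none is specified.
- **Secondary outcomes.** The equal-weight argument does not carry over to spirometry, whose hypothesis is stated for each day. The standard-error argument does.
- **Timing.** Version 6 already revised the primary analysis, so a further change needs a documented reason.

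**Conclusion.** The point holds as a modest, cheaply avoided weakness. AR(1) without a robust standard error is an unneeded restriction. Type I error for the primary test ranges from about 4.4%, through 5.3 to 5.8% for moderate departures, to about 6.6% if correlation is exchangeable; for a four-period opioid model it can reach about 8%. These figures assume complete data, equal daily variances, a common-effect fit and a single test at 1.96 rather than the interim boundaries. Unequal daily variances raised the three-day figure to at most 6.8% in the cases tried.

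If the overall effect comes from a common-effect fit, the reported ratio can differ from the three-day average whenever daily effects differ. The documents do not show that it will.

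**What to change.** Amend the Primary analysis section to specify:

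1. An unstructured covariance over POD 1 to 3 (6 parameters against 2) with Kenward-Roger degrees of freedom, also at the 66-patient interim. Without a small-sample correction, an unstructured common-effect fit gave 6.2 to 6.5% at that size.
2. Day and treatment-by-day terms.
3. The equally weighted POD 1 to 3 contrast of log OBAS as the primary test and the reported geometric mean ratio. This contrast is what restores equal weights; unstructured covariance alone does not, since it reproduces the weights of Step 2 if AR(1) is true.
4. AR(1) as a sensitivity analysis.

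Use the unstructured covariance for the opioid and spirometry models as well, for the standard-error reason only.

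The cost is about 1% in interval width if AR(1) is exactly true, plus a dated amendment giving the reason. N = 196 stands.

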The Blood samples will be collected into K2EDTA tubes and will be centrifuged at 1000 to 1200g for 10 min to obtain plasma within 1 hour of collection. After centrifugation, the plasma will be transferred into polypropylene tubes. The plasma samples will be stored frozen at -20°C or colder until shipment. All samples will be shipped frozen with dry ice to ABS Laboratories, Inc. The shipment address is as follows: [name] ABS Laboratories, Ltd. [name]

Descriptive and Safety Outcomes

- a) Total ICU length of stay;
- b) Hospital length of stay;
- c) Cumulative non-opioid analgesics included acetaminophen, ketorolac, ibuprofen, gabapentin, and pregabalin will be recorded and compared over the initial three postoperative days;
- d) Anxiolytics such as alprazolam, lorazepam, and diazepam will be recorded and compared.

Statistical analysis

We will compare groups on potentially confounding demographic and preoperative risk factors listed in Table 1 using appropriate summary statistics (i.e., mean ± standard deviation, median [Q1, Q3], or N (%) as appropriate) as well as surgical and intraoperative data will be collected prospectively (Table 2). Randomized groups will be compared on balance on these characteristics using absolute standardized difference, defined as the absolute difference in means, mean ranks, or proportions divided by the pooled standard deviation.

Analyses will be modified intent-to-treat, including all randomized patients who received PECSII/serratus blocks (regardless of whether it's consistent with the randomization).

We will summarize descriptive and safety outcomes by randomized groups using appropriate summary statistics (i.e., mean \pm standard deviation, median [Q1, Q3], or N (%) as appropriate). No statistical tests will be performed on these outcomes.

We will use an alpha of 0.05 for both the primary and secondary analyses, with a significance criterion of 0.05 for the primary analysis and 0.0167 for each secondary analysis (i.e., 0.05/3, Bonferroni correction). Analyses will be completed using SAS version 9.4 or newer (SAS Institute, Carey, North Carolina) or R version 3.2.4 or newer (R Project for Statistical Computing, Vienna, Austria).

Primary analysis

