We will estimate the effect of PECS/SAP blocks on FEV_1 , FVC and peak flow rate using three separate repeated measures regression models with an autoregressive correlation structure, adjusting for baseline FEV_1 , FVC, peak flow rate and imbalanced confounders (if any).

The Wald tests for regression model coefficients will be used to test each of the secondary hypotheses; the Bonferroni correction for four outcomes will be employed to control the overall Type I error rate at 0.05 for the secondary outcomes.

Exploratory Analysis

Two separate linear regression models will be developed to assess the relationship between analgesia strategy and each of the two exploratory outcomes (quality of recovery after anesthesia survey and persistent postoperative surgical pain). To compare patients from two groups on these outcomes mean difference will be reported along with 95% confidence intervals.

Descriptive and Safety Analyses

We will summarize descriptive and safety outcomes by randomized groups using appropriate summary statistics (i.e., mean \pm standard deviation, median [Q1, Q3], or N (%) as appropriate). No statistical tests will be performed on these outcomes.

Sample Size Considerations

Per Mamoun, observed a coefficient of variation (CV) of 53% in the placebo group of cardiac surgery patients.⁵⁹ We assumed a slightly more conservative CV of 50% and that the treatment effect favored PECS/SAP blocks by 20% (i.e., true ratio of geometric means of 0.80). We will need to enroll approximately 192 patients (96 per group) to have 90% power at the 0.05 significance level to detect superiority of PECS/SAP blocks to standard routine parenteral and enteral analgesia in patients recovering from MICS .

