We also plan for two interim analyses at 1/3 and 2/3 of the planned enrollment to assess safety, feasibility and formal efficacy and futility. Therefore, interim adjusted sample size is N=98 patients per group, or N=196 total. We will use the conservative gamma spending function with parameters -5 and -5 for alpha (efficacy) and beta (futility), respectively. If the alternative hypothesis is true (the treatment effect exists) there will be a cumulative probability of 10%, 53% and 100% of crossing either an efficacy or futility boundary at the 1st, 2d and final analyses, respectively (Table A and Figure 1 below contains boundary Information). Planned first and second interim analyses will be performed upon accrual of 66 and 132 patients respectively. **Therefore, planned number of patients for the analysis is N=98 patients per group, or N=196 total.**

We will also enroll at least 5 pilot patients in the beginning of the study to test the feasibility of protocol adherence and data collection.

Table A. Boundary Information for interim analysis (3 analyses = 3 stages):

Boundary Information (Standardized Z Scale)**Null Reference = 0**

Stage	Information Level	Alternative		Boundary Values				
		Reference	Lower	Lower	Upper	Beta	Beta	
	Proportion	Lower	Upper	Alpha	Beta	Beta	Alpha	
1		0.3333	-1.88730	1.88730	-3.18319	-0.02167	0.02167	3.18319
2		0.6667	-2.66904	2.66904	-2.64022	-0.53609	0.53609	2.64022
3		1.0000	-3.26890	3.26890	-1.97517	-1.97517	1.97517	1.97517

Figure 1. Boundary plot

[figure not shown]

Table 1: Patient demographic and preoperative risk factors

Sex
Age (years)
Surgery Type (Robot MVR, thoracotomy MVR, AVR through RAT)
Coronary Artery Disease
Hypertension
Pervious Myocardial infarction
Peripheral Arterial Disease
Previous vascular surgery
Smoker (current or former)
Cerebrovascular disease
Diabetes mellitus

Renal failure: Indicate whether the patient has 1) a documented history of renal failure and/or 2) a history of creatinine > 2.0. Prior renal transplant patients are not included as pre-op renal failure unless since transplantation their creatinine has been or currently is > 2.0.
Left ventricular EF

Table 2: Surgical, intraoperative and postoperative data

Time on CPB
X-clamp time
RBCs
Plt
FFP
Cryo
Inotropes in the OR
Time to extubation
Length of ICU stay
Length of hospital stay

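### Covariates for the OBAS, opioid and spirometry models are chosen by observed imbalance, with no cut-off and no statement of which model is used at the interim looks

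*Combined protocol and SAP*

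**What the plan says.** The Statistical analysis section starts from "potentially confounding demographic and preoperative risk factors listed in Table 1" and, in the same sentence, the surgical and intraoperative data of Table 2. It then states: "Randomized groups will be compared on balance on these characteristics using absolute standardized difference". No value is given above which a variable counts as imbalanced.

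The Primary analysis is a "repeated measures linear regression model with an autoregressive correlation structure", fitted to log OBAS, "adjusting for ALL imbalanced confounders (if any". No covariate is named in advance for this model. The opioid model in Secondary Analysis likewise adjusts for whichever baseline or surgical characteristics turn out imbalanced. The spirometry models always include baseline lung function, and beyond that again adjust for "peak flow rate and imbalanced confounders (if any".

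Sample Size Considerations adds formal efficacy and futility testing: "Planned first and second interim analyses will be performed upon accrual of 66 and 132 patients respectively". The Z-values are compared with Table A. The section does not say which model produces them or whether the covariate set is fixed across looks.

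**The concern.** In a randomized trial a baseline difference between groups is chance. Adjusting for a covariate improves the treatment estimate to the extent that the covariate predicts the outcome, whether or not it is balanced. A rule based on imbalance can bring in a variable unrelated to OBAS because it happens to differ, and leave out one that predicts OBAS because it happens not to. The plan already follows the better principle once, by fixing baseline lung function in the spirometry models.

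Two things are at stake. One is precision that the collected data could supply. The other is specification: with no cut-off, the model behind the primary p-value is unknown until the groups have been compared, and the plan does not say how this works at the looks at 66 and 132 patients.

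**Working it through.** **Inputs from the protocol.** "true ratio of geometric means of 0.80"; CV 50%; two-sided alpha 0.05 (Table A is symmetric); 90% power; 96 per group, or 98 per group with interims; looks at 66, 132 and 196 patients; Table A boundaries; 13 variables in Table 1.

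**Reproducing the plan's figure.** On the log scale SD = √ln(1 + 0.5²) = 0.4724 and the effect is |ln 0.80| = 0.2231.
- n per group = 2(1.960 + 1.282)² × 0.4724² / 0.2231², which rounds up to 95. The noncentral t gives 96, so 192 in total reproduces.
- Table A also reproduces: overall type I error 0.050, power 90.0% at drift 3.2689, and cumulative crossing probabilities of 10% and 53% at the first two looks.
- This calculation takes no credit for covariates.

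**How many variables would be called imbalanced by chance.** The SD of a standardized difference is about √(4/N). The cut-offs 0.1 and 0.2 are assumptions, since the plan gives none.

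| N | P(over 0.1) | P(over 0.2) |
|---|---|---|
| 66 | 0.685 | 0.417 |
| 132 | 0.566 | 0.251 |
| 196 | 0.484 | 0.162 |

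Surgery type should be nearly constant under the current inclusion criteria, and exclusion 16 removes most renal failure. That leaves 11 of the 13 variables. Multiplying by 11 gives expected counts of 7.5, 6.2 and 5.3 (cut-off 0.1), or 4.6, 2.8 and 1.8 (cut-off 0.2). These treat the variables as roughly normal; most are in fact binary.

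**Power under each rule.** Trials of 98 per group were simulated with looks at 66, 132 and 196, Table A boundaries, one averaged log-OBAS value per patient and 13 independent normal candidates. Under the imbalance rule the set was re-selected at each look; that is a modelling assumption. With three prognostic candidates (Monte Carlo error about 0.4 points on power):

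| Assumed joint R² | Cut-off | Fixed prognostic list | Imbalance rule | Difference |
|---|---|---|---|---|
| 0.1 | 0.1 | 92.4% | 90.3% | 2.1 |
| 0.1 | 0.2 | 92.8% | 89.8% | 3.0 |
| 0.2 | 0.1 | 95.3% | 92.6% | 2.7 |
| 0.2 | 0.2 | 94.8% | 91.0% | 3.8 |

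Separate simulations with two prognostic candidates agree:
- R² 0.1: 92.9% against 90.5%, a difference of 2.4.
- R² 0.2: 95.4% against 91.8–92.4%, a difference of 3.0–3.6.
- R² 0: 89.5% with the two covariates fixed, 89.8% unadjusted and 87.5–88.7% under the imbalance rule. The rule therefore costs 0.8–2.0 points against the fixed list, through the unrelated variables it adds.

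With a stricter cut-off of 1.96√(4/n), the difference was 2.0 points at R² 0.1 and 4.9 at R² 0.2.

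**Type I error.** In the three-covariate simulations the imbalance rule gave 4.4–4.6% at R² 0.1 and 4.0–4.1% at R² 0.2 (cut-offs 0.1 and 0.2). The fixed list gave 4.9–5.2%.

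**If the chosen covariates are weak.** The closed form at 98 per group, without interims, is Φ(3.307/√(1 − R²) − 1.960). It gives 91.1% at R² 0, 91.6% at R² 0.02 and 92.4% at R² 0.05. The gain over no adjustment is then 0.5 to 1.3 points.

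**The case against.** The case for leaving the text alone has some force.

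- **Wording.** The plan speaks of confounders, a term that implies a relation to outcome, so it need not mean every variable that differs. But no step in the plan establishes that relation. The only operational test is the standardized difference.
- **Power.** A reader might infer that the trial is underpowered. The documents do not support that: the sample size assumes no covariate gain, and power under the rule stayed near 90% or above when prognostic covariates existed. The loss is relative to a better model.
- **Benchmark.** The 92–95% figures assume that the fixed list is exactly the prognostic set. Nothing in the protocol links age or sex to OBAS. This stands, and it limits the promised gain.
- **Interim looks.** A reader might infer that covariates are re-chosen at each look, so that Table A receives Z-values from different models. The protocol neither says this nor rules it out. What stands is the silence.
- **Type I error.** A reader might infer inflation. None was seen when a set cut-off was applied automatically. Inflation (5.8–6.6%) appeared only in a deliberate worst case, where the choice among no adjustment, cut-off 0.1 and cut-off 0.2 followed the largest |Z| at each look. The protocol describes no such practice; a fixed list would exclude it.
- **Timing.** The current version is dated July 2022, and the documents do not say whether the interim looks had already taken place. A completed look cannot be re-specified.

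**Conclusion.** The point holds as a matter of efficiency and specification. The selection criterion is observed imbalance rather than expected relation to outcome, it has no cut-off, and the interim model is not stated. Against a fixed prognostic list the rule gives up about 2 to 4 points of power if covariates explain 10% to 20% of log-OBAS variance, and about 1 to 2 points if they explain little or nothing. These sizes rest on assumed R², assumed cut-offs of 0.1 and 0.2, independent normal covariates and automatic re-selection at each look. The planned 90% is roughly kept, and the test is at most mildly conservative. The change is worth making because it is nearly free, not because the primary result would otherwise be invalid.

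**What to change.** In Primary analysis and Secondary Analysis, replace the imbalance wording with a short fixed list of pre-randomization variables from Table 1. The investigators should choose it for expected relation to OBAS; age and sex are an example. Include the list whether or not the groups differ on it, and keep each spirometry model's own baseline value. State that the same model supplies the Z-value at the final analysis and at any interim look not yet done. Keep the absolute standardized differences for description only.

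The variables are already collected, so no patients, visits or procedures change. The statistical cost is about two degrees of freedom out of about 190. If the chosen variables are weakly prognostic, the gain may be 1 point or less. If interim looks have already been done, record which model was used there and date the change.
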